5.1.6 Restrictions During the Study

See [Section 5.1.3 Previous and Concomitant Treatment] for prohibited medications.

02 Dec 2019 Astellas Page 55 of 111

5.2 Demographics and Baseline Characteristics

5.2.1 Demographics

Demographic information will be collected for all subjects (where permitted) at the screening visit and will include age, date of birth, sex, race and ethnicity.

5.2.2 Medical History

Medical history will be collected at the screening visit in order to assess Inclusion/Exclusion criteria and will be reconfirmed prior to study immunization (if screening was performed > 7 days from study immunization [day 1]).

5.3 Immunogenicity Assessments

The immunogenicity assessments described below are accepted surrogates for efficacy in pneumococcal vaccine studies.

5.3.1 Immunological Response

Considering its mechanism of action, ASP3772 is expected to induce the immune response to pneumococcal PS and carrier proteins, the antigens present in ASP3772. Blood samples to assess immunogenicity will be collected as indicated in the Schedule of Assessments [Table 1, Table 2 and Table 3]. Immunogenicity assessments will be performed from blood samples collected at the dosing visit (day 1) prior to study immunization and at the 7-day and 30-day follow-up visits. Immunogenicity data will be provided to the investigative site when available.

Immunogenicity of ASP3772 will be evaluated by measuring serotype-specific anticapsular IgG antibody concentrations by multiplex direct Luminex immunoassays and OPA titers against the 24 vaccine serotypes in serum samples. OPA measures the functional killing activity of antibodies against the pneumococcal serotypes. In addition, pneumococcal carrier protein (SP1500+0785)-specific immune response will be assessed by measuring specific IgG in serum and activity against non-vaccine serotypes. Thelper 17 cells (Th17) response to SP1500+0785 will be evaluated by measuring interleukin (IL)-17.

blood mononuclear cells (PBMCs) as exploratory assessments.

Details on sampling, processing and storage will be described in the laboratory manual. Samples will be shipped on dry ice to a designated contract research organization (CRO) for the analyses.

5.4 Safety Assessment

5.4.1 Adverse Events

All observed or spontaneously reported AEs will be documented. TEAEs and MAAEs (including PIMMCs and NOCDs) will be assessed throughout the study, from the time of dosing (day 1) up to the last follow-up visit (day 30 for Group 3; day 180 for Groups 1 and

02 Dec 2019 Astellas Page 56 of 111

2). Details of definitions and reporting of AEs (including TEAEs, MAAEs, PIMMCs and NOCDs) and SAEs are provided in [Section 5.5 Adverse Events and Other Safety Aspects].

5.4.2 Vital Signs

Vital signs (body temperature, blood pressure and pulse rate) will be measured at screening, the dosing visit (day 1) and at each subsequent visit (day 7 and day 30 [all groups]). On day 1, vital signs (body temperature, blood pressure, pulse rate and respiration rate) will be collected pre-dose and 30 min and 1 hour post-dose. Vital signs will be collected after the subject has been in seated position for at least 5 minutes. When vital signs are scheduled for the same time as blood sample or study vaccine administration, then vital signs will be taken first. Blood pressure should be obtained using the same cuff size and the same arm. Abnormal findings will be documented as clinical events through day 7 and AEs post day 7.

Subjects will be instructed to measure and record in the electronic diary their body temperature daily through day 7. Subjects will also be instructed to measure and record their body temperature in case of illness and contact the site if elevated.

5.4.3 Reactogenicity

Subjects will remain at the study site 60 minutes after the injection for safety evaluation. Subjects may be discharged after 60 minutes at the discretion of the investigator. Local and systemic reactogenicity will also be reported for each of 7 consecutive days following the study injection.

Reactogenicity will be assessed using solicited adverse reactions from the time of immunization (day 1) up to 7 days postimmunization. These include local and systemic reactions with a protocol-specified predefined grading scale (see [Appendix 12.6 Grading of Local Reactogenicity; Appendix 12.7 Grading of Signs of Systemic Reactogenicity; and Appendix 12.8 Grading of Laboratory Abnormalities]). Local reactions are pain, tenderness, redness/erythema and swelling/induration. Systemic reactions are nausea/vomiting, diarrhea, headache, fever, fatigue, joint pain or arthralgia and muscle discomfort or pain/myalgia. The daily maximum measurement of local and systemic reactogenicity signs will be recorded by the subject during the 7-day period using an electronic subject electronic diary. For Stage 1, subjects will be questioned at the day 7 visit if they experienced any joint pain/arthralgia through their day 7 visit postimmunization. If their response is yes, they will be asked to provide the degree of severity using a 4-category grading scale from 1 (no interference with activity) to 4 (ER visit or hospitalization) as per Appendix 12.7. For Stage 2, assessments of joint pain/arthralgia will be collected daily through day 7 using the electronic diary. All subjects will be questioned if they experienced any other illness through day 7 postimmunization on their day 7 visit. Reactogenicity reactions will be reported as Clinical Events. If the reactogenicity reaction extends beyond 7-day period or if serious, it will be recorded as an AE, and followed until resolution or deemed medically stable. Subjects will be instructed to contact the site during the 7 consecutive days following an injection to report any reaction \geq grade 2. All local and systemic reactions \geq grade 3 require confirmation by a health care professional.

5.4.4 Laboratory Assessments

Laboratory assessments will be performed at the screening visit and at study immunization (if screening was performed > 7 days from study immunization [day 1]). Assessments will be repeated at follow-up visits on day 7 and day 30. See [Appendix 12.5 Laboratory Assessments] for details of laboratory tests.

Clinical significance of out-of-range laboratory findings is to be determined and documented by the investigator/subinvestigator who is a qualified physician.

5.4.5 Anti-biotin Antibodies

Anti-biotin antibodies will be measured from serum samples on day 1 prior to study immunization and at day 30 follow-up visit for Group 1 and Group 2 subjects. Serum anti-biotin antibodies will be repeated on day 180 if tested positive on day 30. In subjects with positive serum anti-biotin antibodies, serum biotin levels will be measured in the same sample.

5.4.6 Physical Examination

A physical examination consisting of an examination of general appearance, eyes, nose throat, neck (including thyroid), lymph nodes, chest, lungs, cardiovascular, abdomen, skin, extremities, musculoskeletal and neurological system including mental status will be conducted at the screening visit, prior to study immunization (day 1) and at the day 30 follow-up visit. A symptom-directed physical exam may be performed at any other time, if necessary. The screening physical examination also includes evaluation of significant, ongoing medical conditions. Any changes between screening and randomization will be captured in the medical/surgical history.

Any abnormal finding(s) at screening must not be exclusionary per the eligibility criteria and must be assessed and documented as not clinically significant if a subject is to be enrolled in the study. After receiving the study vaccine, new abnormal findings or a worsening of an ongoing abnormal condition will be recorded as an SAE or AE ([S]AE).

5.4.7 Electrocardiogram

Standard 12-lead ECG recordings will be used for the purposes of safety assessment and subject management by the Investigator.

A 12-lead, resting ECG is to be recorded at each timepoint as indicated in Table 1, Table 2 and Table 3 (Schedule of Assessments). Subjects should remain supine for at least 5 minutes prior to all ECGs. Dates and times may be generated by the machine's internal clock and are considered source data. The results are to be interpreted by qualified personnel in real time for the management of the subjects' clinical condition. The principal investigator/designee will initial and date, and provide his/her clinical interpretation on each report. The results (normal, abnormal not clinically significant, abnormal clinically significant) are to be recorded in the electronic case report forms (eCRFs).

The ECG recorded during screening will be used to determine eligibility for study participation. Subjects who have a clinically significant abnormal ECG will not be eligible

for the study. The interpretation of the ECG from screening will be the baseline to which post-study vaccine dosing ECGs will be compared.

Unscheduled ECGs will be performed if clinically indicated.

If a machine-read corrected QT interval exceeds 500 msec after repeat measurement, this should be reported as an AE.

The original print-out and an electronic copy of all scheduled and unscheduled ECG tracings should be maintained on site as source data.

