After both sentinel subjects in a cohort have completed study procedures on day 7, the decision to open enrollment for the full cohort will be determined by DEC based on review of the Day 7 reactogenicity and safety data of those 2 sentinel subjects.

After all vaccinated subjects in a cohort have completed study procedures on day 7, the decision to dose escalate to next cohort within both stages will be determined by DEC based on the review of the following:

- Day 7 reactogenicity and safety data (AEs, ECG, clinical laboratory tests, vital signs) from the current cohort.
- Day 7 reactogenicity and safety data from all subjects of the preceding cohort(s).

To evaluate safety by DEC, day 7 data is needed from a minimum of 38 subjects in each cohort for Stage 1.

Stage 2 will commence based on DEC review of the following:

- Day 7 reactogenicity and safety data (AEs, ECG, clinical laboratory tests, vital signs) from all subjects in Stage 1.
- Day 30 safety data (AEs, ECG, clinical laboratory tests, vital signs) from all subjects in Stage 1.

To evaluate safety by DEC, day 7 data is needed from a minimum of 129 subjects in each cohort for Stage 2. Further details around the dose escalation process are included in the DEC charter.

Dose Escalation Criteria:

Depending on the nature, frequency and severity of the safety profile observed in the study, and the study vaccine received, the DEC will decide whether to:

- Proceed with dose escalation.
- Proceed from Stage 1 to Stage 2.
- Determine need of sentinel dosing in Stage 2 cohorts.
- Stop dose escalation.

Dose escalation may proceed unless 1 (or more) of the following apply in subject(s) receiving ASP3772:

- Two or more subjects experience an AE of severe intensity related to ASP3772 or 2 or more subject(s) experience a reactogenicity event of grade 3 or higher intensity related to ASP3772.
- One or more subject(s) experience a SAE related to ASP3772.

02 Dec 2019 Astellas Page 22 of 111

Endpoints for Evaluation:

Stage 1:

Primary Endpoints

Safety and tolerability of ASP3772 will be assessed by:

- Treatment-emergent adverse events (TEAEs) including MAAEs, PIMMCs, NOCDs
- Vital signs (body temperature, blood pressure and pulse rate)

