Visit Days (Window)	-28 to -3	1	7 (+1)	30 (±2)*	180 (±14)§
Informed Consent ^b	X				
Inclusion/Exclusion Criteria	X	X†			
Randomization ^c		X†			
Demographics	X				
Medical History ^d	X	Χţ			
Physical Examination ^e	X	X†		X	
Routine 12-lead ECG	X	Χţ	X	X	
Virology ^f	X				
Urine Drug Screen ^g	X	X†			
Pregnancy Test ^h	X	X†		X	
Height, Body Weight	X				
Study Immunization		X			
Vital Signs (blood pressure, pulse rate, body temperature) ⁱ	X	X†	X	X	
Clinical Laboratory Tests (hematology biochemistry, coagulation profile, hepatic profile, urinalysis) ^j	X	X†‡	X	X	
Serum sample for Immunogenicity		Χţ		X	
Serum sample for Anti-biotin Antibodies		X†		X	X^{l}
Whole-blood sample for T-cell Immune Response Measurement		Χţ	X	X	
Prior/Concomitant Medication ⁿ				\rightarrow	
Reactogenicity ^o		<	\longrightarrow		
AEsp					
SAEs ^p	<				
MAAEs including PIMMCs and NOCDs ^p		<			\longrightarrow

AE: adverse event; ECG: electrocardiogram; MAAE: medically attended adverse event; NOCD: new-onset chronic disease; PIMMC: potential immune-mediated medical conditions; SAE: serious adverse event; WBC: white blood cell.

Footnotes continued on next page

02 Dec 2019

Astellas

Page 29 of 111

- CONFIDENTIAL -
- † To be performed prior to administration of study vaccine. **Note:** Vital signs will also be performed after the administration of the study vaccine.
- \ddagger Not required if collected at a screening visit, which is ≤ 7 days from dosing visit.
- § Visit conducted as a phone call unless anti-biotin antibodies were elevated at day 30 visit.
- * If a subject has received any systemically absorbed antibiotics between day 1 and day 30, the visit should take place at least 7 days after the last dose of the antibiotics.
- a. Screening will be completed up to 28 days prior to study immunization. Subjects will be assigned a subject number for use throughout the study at the screening visit via the Interactive Response Technology (IRT) system
- b. Informed consent must be obtained prior to the performance of any study-related procedure and before Randomization.
- c. Subjects will be randomized via the IRT at the dosing visit.
- d. Medical history will be collected at screening in order to assess Inclusion/Exclusion criteria and will be reconfirmed prior to study immunization.
- e. A physical examination will be performed at the screening visit (days -28 thru -3), prior to study immunization (day 1) and day 30 visits.

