o. Subject must remain at site for the first 60 minutes following the injection. Local reactogenicity will be evaluated at 1 hour by site staff and entered into an electronic diary by the subject while on site. The subject will evaluate local and systemic reactogenicity symptoms except for joint pain/arthralgia as per Appendix 12.7 daily and record the results in the electronic diary daily through day 7 following study immunization. On day 7, subject will be questioned if he/she experienced any joint pain/arthralgia or other illness, which is not incorporated into the reactogenicity assessment, in the electronic diary.

p. All observed or spontaneously reported AEs, inclusive of MAAEs, PIMMCs and NOCDs will be documented,. AEs will be assessed at the study immunization visit, before and approximately 60 minutes after immunization. MAAEs will be reported through day 180. The investigator will avoid leading questions to influence reporting of AEs.

Table 2 Schedule of Assessments - Stage 2: Subjects 65 to 85 Years of Age, PCV13 Naïve (Group 2)

Assessments	Screeninga	Dosing 2	Follow-up		
Visit Number	1		3	4	5
Visit Day (Window)	-40 to -3	1	7 (+1)	30 (±2)*	180 (±14)§
Informed Consent ^b	X				
Inclusion/Exclusion Criteria	X	X†			
Randomization ^c		Χţ			
Demographics	X				
Medical History ^d	X	Χţ			
Physical Examination ^e	X	Χţ		X	
Routine 12-lead ECG	X	Χţ	X	X	
Virology ^f	X				
Height, Body Weight	X				
Study Immunization		X			
Vital Signs (blood pressure, pulse rate, body temperature) ^g	X	Χţ	X	X	
Clinical Laboratory Tests (hematology, biochemistry, coagulation profile, hepatic profile, urinalysis) ^h	X	X†‡	X	X	
CCI					
Serum sample for Immunogenicity ^j		X†		X	
Serum sample for Anti-biotin Antibodies		Χ†		X	X^k
Whole-blood sample for T-cell Immune Response Measurement		Χ†	X	X	
Prior/Concomitant Medication ¹					
Reactogenicity ^m			\rightarrow		
AEs ⁿ				\rightarrow	
SAEs ⁿ					
MAAEs including PIMMCs and NOCDs ⁿ					

Footnotes appear on next page

- CONFIDENTIAL -

AE: adverse event; ECG: electrocardiogram; MAAE: medically attended adverse event; NOCD: new-onset chronic disease; PCV13: Prevnar 13; PIMMC: potential immune-mediated medical conditions; SAE: serious adverse event; WBC: white blood cell.

- † To be performed prior to administration of study vaccine. **Note:** Vital signs will also be performed after the administration of the study vaccine.
- ‡ Not required if collected at a screening visit, which is \leq 7days from dosing visit.

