- § Visit conducted as a phone call unless anti-biotin antibodies were elevated at day 30 visit.
- * If a subject has received any systemically absorbed antibiotics between day 1 and day 30, the visit should take place at least 7 days after the last dose of the antibiotics.
- a. Screening will be completed up to 40 days prior to study immunization. Subjects will be assigned a subject number for use throughout the study at the screening visit via the Interactive Response Technology (IRT) system.
- b. Informed consent must be obtained prior to the performance of any study-related procedure and before randomization.
- c. Subjects will be randomized via the IRT system at the dosing visit.
- d. Medical history will be collected at screening in order to assess Inclusion/Exclusion criteria and will be reconfirmed prior to study immunization.
- e. A physical examination will be performed at the screening visit (days -40 thru -3), prior to study immunization (day 1) and day 30 visits.
- f. Perform tests for Hepatitis B surface antigen (HBsAg), hepatitis A virus antibodies (immunoglobulin M), HCV antibody (anti-HCV) confirmed by reflex testing (HCV-RNA) and HIV antigen/antibody (type 1 and/or type 2) at screening.
- g. Body temperature, blood pressure and pulse rate will be assessed in a sitting position. At the dosing visit, body temperature, blood pressure, pulse rate and respiratory rate will assessed predose at approximately 30 min and 1 hour postdose. Predose vitals should be collected close to the immunization and should not be more than 30 minutes prior to the dose administration. Body temperature will be collected by the subject daily through day 7 following the study immunization.
- h. Perform test for hematology (hemoglobin, hematocrit, erythrocytes, leukocytes, differential WBC, platelets), biochemistry (sodium, potassium, calcium, chloride, glucose, total cholesterol, triglycerides, blood urea nitrogen, creatinine, total protein, albumin, c-reactive protein), coagulation profile (prothrombin time, activated partial thromboplastin time, fibringen), hepatic profile (alkaline phosphatase, aspartate transaminase, alanine transaminase, y-glutamyltransferase, total bilirubin, lactate dehydrogenase), urinalysis (using dipstick - protein, glucose, pH, blood, leukocytes, urobilinogen, bilirubin, ketones, nitrite, urine microscopy [optional]).

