7 STATISTICAL METHODOLOGY

A statistical analysis plan (SAP) will be written to provide details of the analysis, along with specifications for tables, listings and figures to be produced. The SAP will be finalized before the database soft lock at the latest. Any changes from the analyses planned in SAP will be justified in the clinical study report.

In general, continuous data will be summarized with descriptive statistics (number of subjects, mean, standard deviation, geometric mean and geometric standard deviation (GSD) where applicable, minimum, median and maximum), and frequency and percentage for categorical data. Percentages by categories will be based on the number of subjects with no missing data, i.e., the percentages will sum to 100%.

Baseline will be defined as the last observation prior to first dose, unless otherwise specified.

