6.2.1.5 ECGs

ECGs will be collected at screening for all groups at Screening for all groups and at Day 7 for Groups 1 and 2, those randomized to PCV13 or ASP3772. ECGs will be graded as ‘normal’, ‘abnormal-not clinically significant’, and ‘abnormal-clinically significant’. Any abnormal ECGs that have worsened since screening/baseline will be recorded as an adverse event.

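### Post-vaccination ECGs are judged against the screening ECG although a pre-dose Day 1 ECG is scheduled in every group, and the ECG visit list in SAP 6.2.1.5 contradicts the SAP's own schedules; the effect is likely small

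*Protocol*

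**What the plan says.** Protocol 5.4.7 fixes the reference for ECGs: "The interpretation of the ECG from screening will be the baseline to which post-study vaccine dosing ECGs will be compared". The general rule in protocol section 7 is different: "Baseline will be defined as the last observation prior to first dose, unless otherwise specified". The SAP follows the general rule for laboratory tests (7.5.3) and vital signs (7.5.4), where baseline is the last value before the vaccine.

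In protocol Tables 1 to 3 the row "Routine 12-lead ECG" has an entry on Day 1 in every group, marked with the dagger footnote "To be performed prior to administration of study vaccine". Day 1 laboratory tests may be skipped if screening was no more than 7 days earlier; the ECG row carries no such waiver. The screening window is wide. For Stage 2, "Screening will be completed up to 40 days prior to study immunization"; for Stage 1 the limit is 28 days.

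SAP 6.2.1.5 gives its own visit list: "ECGs will be collected at screening for all groups at Screening for all groups and at Day 7 for Groups 1 and 2". It then sets an AE rule: "Any abnormal ECGs that have worsened since screening/baseline will be recorded as an adverse event". Day 30 ECGs have a stated use: the DEC's review before Stage 2 includes "Day 30 safety data (AEs, ECG, clinical laboratory tests, vital signs) from all subjects in Stage 1".

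**The concern.** The comparison is meant to show what changed after vaccination. With the screening ECG as reference, it also takes in whatever changed in the days or weeks before vaccination, although the trial records an ECG that could separate the two. No text gives the Day 1 ECG a role in the analysis, and no reason is given for departing from the general baseline rule.

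The error can run in both directions. A new abnormality that was already present before the injection can be dated after it. A change that did follow the injection can be hidden if it merely restores the state seen at screening.

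This bears on TEAEs, which are a primary endpoint (protocol 2.3) and are defined as AEs observed from immunization to 30 days (protocol 7.5.1, SAP 6.2.1.1). Separately, the SAP 6.2.1.5 visit list, read alone, leaves Group 3 without any post-vaccination ECG.

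**Working it through.** The plan states no figure on this point, so there is none to reproduce. The check sets the texts side by side and does the date arithmetic.

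**1. ECGs scheduled and ECGs named**

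| ECG | Groups | Protocol and SAP Tables 1–3 | SAP 6.2.1.5 | Role under protocol 5.4.7 |
|---|---|---|---|---|
| Screening | all | yes | yes | eligibility and baseline |
| Day 1, pre-dose | all | yes | not named | none stated |
| Day 7 | 1 and 2 | yes | yes | compared with screening |
| Day 30 | all | yes | not named | compared with screening |

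For Group 3, Day 30 is the only scheduled post-vaccination ECG.

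**2. Greatest age of the reference ECG.** With immunization on Day 1, age = lead time + (visit day − 1).

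- Stage 1, lead 28 days: 28 at dosing; 28 + 6 = 34 at Day 7 (35 at the +1 limit); 28 + 29 = 57 at Day 30 (59 at +2).
- Stage 2, lead 40 days: 40 at dosing; 40 + 6 = 46 at Day 7, Group 2 only (47 at +1); 40 + 29 = 69 at Day 30 (71 at +2).
- Day 1 ECG as reference: 6 days at Day 7 (7 at +1) and 29 at Day 30 (31 at +2), in both stages.

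These are maxima, since screening may be as late as Day −3.

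**3. Two sequences on the three-category ECG scale**

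| Screening | Day 1 pre-dose | Day 7 | Against screening | Against Day 1 |
|---|---|---|---|---|
| normal | abnormal, not clinically significant | same as Day 1 | worsened: AE under SAP 6.2.1.5 | no change |
| abnormal, not clinically significant | normal | abnormal, not clinically significant | no change | worsened |

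**4. Which rule makes it an AE.** SAP 6.2.1.5 asks only that an abnormal ECG has worsened. Protocol 5.5.1 accepts a test abnormality as an AE only if it causes signs or symptoms, needs intervention, leads to interruption or discontinuation of study medication, or is clinically significant in the investigator's opinion. Protocol 5.5.1.1 adds that a clinically significant finding tied to underlying disease is generally not reportable. The first sequence above is an AE under the SAP sentence, but not under protocol 5.5.1 unless one of its other criteria is met.

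**5. Possible size.** The documents give no rate of ECG worsening between screening and Day 1. Assume q = 0.5% to 5%; expected number = N × q.

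- Group 1: 120 × q = 0.6 to 6.0
- Group 2: 396 × q = 2.0 to 19.8
- Each Stage 2 ASP3772 dose arm, or Group 3: 99 × q = 0.5 to 5.0

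These are upper bounds on misdated AEs under the assumption, because the change must also persist to a later ECG and be recorded as an AE.

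**6. Effect on comparisons and on count-based triggers.** Pooled PCV13 in Stage 2 is 3 × 33 = 99 subjects, so the expected count is again 99 × q. If q is the same in both arms, the expected difference is zero. Protocol 4.4.1 reveals assignments when at least 10% of a cohort has the same or a related AE: 4 of 40 in Stage 1, or 14 of 132 in Stage 2 (10% is 13.2). Even at q = 5% the expected counts are 40 × 0.05 = 2.0 and 132 × 0.05 = 6.6, and those would have to be the same or related events.

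**The case against.** The strongest reply is that little depends on this baseline. Protocol section 7 allows exceptions, so 5.4.7 is a permitted choice. Both documents only list ECG results (section 7.5.5 in each), with no shift or change-from-baseline table. Protocol 2.3 calls ECGs additional safety assessments, and no escalation or stopping criterion is specific to them. The Day 1 ECG is read in real time, AEs are collected from consent, and the causality assessment considers timing, so an investigator can recognize a pre-dose change. Stage 2 admits only healthy subjects or those whose chronic disease has been stable for 12 weeks. SAP 7.7.3 labels the Day 1 visit as baseline, so the screening/baseline wording could include the Day 1 ECG.

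All of this lowers the frequency of error. None of it changes the explicit rule in 5.4.7, requires a later ECG to be checked against Day 1, or resolves the conflict inside the SAP.

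Four stronger readings are tempting, and the documents do not support them:

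- *The SAP drops the Day 1 and Day 30 ECGs, so Day 30 change is never assessed.* Only 6.2.1.5 leaves them out. SAP Tables 1 to 3 schedule both, protocol 5.4.7 requires each scheduled ECG to be interpreted, the DEC reviews Stage 1 Day 30 ECGs, and SAP 7.5.5 lists results without limiting the visits.
- *Every pre-dose change becomes a post-vaccine AE.* That could follow only from the SAP sentence; protocol 5.5.1 and 5.5.1.1 are narrower.
- *The ratio of a 40-day lead to a 7-day follow-up measures the error.* It compares calendar intervals at the widest limit and says nothing about how often ECGs change.
- *The comparison with PCV13 is biased.* Within randomized, observer-blinded cohorts, misdating should fall on both arms alike.

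**Conclusion.** The point holds in a limited form. Protocol 5.4.7 names an older reference ECG when a pre-dose Day 1 ECG is available, against the plan's own practice for other safety measures. Combined with the SAP 6.2.1.5 AE sentence, this can misdate a pre-vaccination change or hide a post-vaccination one. The 6.2.1.5 visit list also contradicts SAP Tables 1 to 3.

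The likely effect is small. It bears on absolute TEAE counts and on Group 3, which has no randomized comparator, rather than on the contrast between ASP3772 and PCV13. The figure of 2 to 20 of 396 in Group 2 is an upper bound on misdated events and rests wholly on the assumed 0.5% to 5%. The expectation of equal effect in the arms assumes similar screening lead times. Randomization supports this within a cohort; for PCV13 pooled over sequential cohorts it also needs lead times to be similar between cohorts. The count-based trigger in protocol 4.4.1 is unlikely to be reached through this alone. It should be corrected because the rule is explicit and the remedy uses data already collected.

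**What to change.** - In protocol 5.4.7 and SAP 6.2.1.5, define the ECG baseline as the last pre-dose ECG: normally Day 1, and screening only if Day 1 is missing. Keep the screening ECG for eligibility.
- Correct the SAP 6.2.1.5 visit list to match Tables 1 to 3: screening, Day 1 and Day 30 in all groups, and Day 7 in Groups 1 and 2.
- Reconcile the AE sentence in SAP 6.2.1.5 with protocol 5.5.1 and 5.5.1.1, so that one rule decides when an ECG finding is an AE.
- So that the screening fallback works in Stage 2, extend the screening window in SAP 7.7.3, which still opens at Day −28, to the 40 days allowed.

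The cost is wording in one protocol section and two SAP sections. The Day 1 and Day 30 ECGs are already scheduled, so no procedure is added.
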